### **AEs by severity**

All adverse events will be summarized by maximum severity, primary system organ class and preferred term. If a patient reports more than one adverse event within the same primary system organ class, only one adverse event will be counted for that patient at the highest severity level in the total row for each primary system organ class. If a patient reported more than one adverse event with the same preferred term, the highest (maximum) severity will be presented. Missing severity will be assumed to be severe in the summary table.

### **AEs leading to permanent study drug discontinuation**

Treatment emergent adverse events leading to permanent study drug discontinuation, regardless of study drug relationship, will be summarized by primary system organ class and preferred term.

### **AEs requiring dose adjustment or interruption**

Treatment emergent adverse events requiring dose adjustment or interruption, regardless of study drug relationship, will be summarized by primary system organ class and preferred term.

### **AEs requiring occurrence of hospitalization**

Treatment emergent adverse events leading to hospitalization, regardless of study drug relationship, will be summarized by primary system organ class and preferred term.

### **Number of hospitalizations**

Summary statistics using frequency and percentage will be provided for number of hospitalizations per patient occurred during treatment period.

### **2.7.2 Serious adverse events**

Number and percentage of patient with serious adverse events, regardless of study drug relationship, will be presented by primary system organ class and preferred term.

SAEs will also be listed separately.

### **2.7.3 Adverse events of special interest / grouping of AEs**

The number (and proportion) of patients with adverse events of special interest/related to identified and potential risks will be summarized by primary system organ class and preferred term.

The following will be considered as an AESI for the study:

1. Infections and Infestations (VZV infections, herpes virus infections),
2. Bradyarrhythmia/bradycardia,
3. Elevated liver functions tests,
4. Malignancies (basal cell carcinoma),
5. Thromboembolic events,

6. Convulsions,
7. Macular edema,
8. Bronchoconstriction,
9. Hypertension

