Due to the occurrence of bradyarrhythmic events during in the Phase I trial, a dose titration was implemented in the Phase II study, resulting in the attenuation of the earlier observed negative chronotropic and dromotropic effects. There were no symptomatic bradyarrhythmic events or asymptomatic AV-blocks of concern following the introduction of the initial-dose titration scheme.

The double-blind registration Phase III EXPAND trial, (N=1651) demonstrated unique effects on SPMS patients (Kappos et al, 2018). The majority of the study population had been on other DMTs prior to entering into the study. In patients randomized to the siponimod arm, approximately 69% of patients had previously been treated with either IFNβ-1a or IFNβ-1b while 26% of patients had been treated with glatiramer acetate. For patients on prior DMTs, there were specific washout requirements implemented without any monitoring during the washout. Given the development of additional S1P receptor modulators over the last few years, transition between S1P treatments has not broadly assessed. Theoretically, while both siponimod and fingolimod demonstrate persistent internalization and enhanced degradation of the S1P-receptor, there is clinical utility in understanding the role of titration, or lack of, when converting between the two S1P therapeutic options to ensure patients are not undertreated.

Safety results from the Phase III trial demonstrated that siponimod is safe and well tolerated

- 197 (18%) patients on siponimod and 83 (15%) on placebo had at least one serious adverse event.
- Headache, nasopharyngitis, urinary tract infection, and falls were the most frequent adverse events, being reported in more than 10% of patients in both treatment groups (siponimod vs placebo)
- Hypertension was reported in 115 patients (10%) on siponimod compared with 41 (8%) on placebo
- Four deaths occurred in each treatment group. Deaths in the siponimod group were due to metastatic gastrointestinal melanoma within 4 months of commencing siponimod; septic shock in a patient with terminal colon cancer; urosepsis more than 10 weeks after discontinuation of siponimod and after two doses of rituximab; and suicide.
- Cardiac effects: 1346 (82%) of 1651 patients underwent continuous mobile cardiac telemetry for up to 6 days.
- During double-blind treatment initiation, the maximum reduction in mean heart rate

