9.1 Discontinuation

9.1.1 Discontinuation of study treatment

Study treatment can be interrupted or discontinued based on investigator's judgement and overall clinical assessment, including in the following cases:

- Adverse event or serious adverse event (e.g., Serious infections, Symptomatic bradyarrhythmia)
- Abnormal laboratory value(s) including liver function tests
- Use of prohibited medications.

All dose changes must be recorded on the Dosage Administration Record eCRF.

Patients may voluntarily withdraw from the study for any reason at any time. They may be considered withdrawn if they state an intention to withdraw, fail to return for visits or become lost to follow up for any other reason. If premature withdrawal occurs for any reason, the investigator must make every effort to determine the primary reason for a patient's premature withdrawal from the study and record this information on the corresponding patient's disposition eCRF page.

Study treatment should be discontinued under the following circumstances:

- Withdrawal of informed consent
- Pregnancy
- Protocol violation that results in a significant risk to the patient's safety
- Non-compliance with study treatment
- Lost to follow up
- Emergence of certain adverse events, such as malignancy (except successfully treated basal cell carcinoma), liver failure or, serious chronic infections (such as HIV).

Note 1: For a patient with a positive urine pregnancy test, study medication must be immediately discontinued and a serum pregnancy test conducted. If the serum test is negative, the patient may restart study medication; if siponimod treatment has been interrupted for 4 or more consecutive daily doses, treatment must be re-initiated with the 5-day titration pack. If the serum test is positive, the patient can either be discontinued from the study or remain in the study continuing all scheduled visits, as above. Restart of study medication after the pregnancy (and lactation) will be considered on a case by- case basis, as above. Women who need another disease modifying treatment during pregnancy will be withdrawn from the study.

Page 71

The investigator must also contact the IRT to register any patient discontinuations from study treatment.

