10.2 Additional Safety Monitoring

10.2.1 Liver safety monitoring

To ensure patient safety and enhance reliability in determining the hepatotoxic potential of an investigational drug, a standardized process for identification, monitoring and evaluation of liver events has to be followed.

Liver events are divided into two categories:

- Liver events of special interest (AESI) which consist of elevations of liver function tests (LFTs)
- Medically significant liver events which are considered as serious adverse events (SAEs) and which consist of marked elevations of LFTs and / or pre-specified adverse events.

Please refer to Appendix 2 for complete definitions of liver events.

Any liver event which meets the criteria for "medically significant" event as outlined should follow the standard procedures for SAE reporting. Every liver event as defined in Table 16-1 of Appendix 2 should be followed up by the investigator or designated personal at the trial site as summarized below:

- Repeating the LFT to confirm elevation as appropriate
- Discontinuation of the investigational drug if appropriate
- Hospitalization of the patient if appropriate
- A causality assessment of the liver event via exclusion of alternative causes (e.g., disease, co-medications)
- An investigation of the liver event which needs to be followed until resolution.

These investigations can include serology tests, imaging and pathology assessments, hepatologist's consultancy, based on investigator's discretion. All follow-up information, and the procedures performed should be recorded on appropriate eCRF pages, including the liver event overview eCRF pages.

NOTE: If local requirements for liver safety monitoring are more stringent than those outlined in this section of the protocol, then the local requirements will take precedence

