10.2.3 Bradycardia

This is considered an AESI. To ensure patient safety and enhance reliability in determining the bradycardia potential of an investigational drug, a standardized process for identification, monitoring and evaluation of bradycardia events has to be followed. (Please see Appendix 7 for instructions)

Bradycardia is defined as any pre-dose HR less 55 bpm or post-dose HR bpm less than 45.

11 Data Collection and Database management

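### No planned table counts the patients who meet the protocol's own heart-rate definition of the bradycardia AESI

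*SAP*

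**What the plan says.** Protocol 10.2.3 says of bradycardia: "This is considered an AESI". It asks for a standardised way of identifying such events and gives a definition based on a reading: "Bradycardia is defined as any pre-dose HR less 55 bpm or post-dose HR bpm less than 45". Protocol 12.5.1 promises a summary of AESIs but does not list them, so SAP 2.7.3 is the working definition.

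SAP 2.7.3 states that patients with "adverse events of special interest/related to identified and potential risks will be summarized by primary system organ class and preferred term". It then names nine categories, bradyarrhythmia/bradycardia among them. It gives no preferred-term or SMQ list for any category and no rule based on a measured value. Two categories carry a parenthesis: "Infections and Infestations (VZV infections, herpes virus infections" and "Malignancies (basal cell carcinoma".

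Measured heart rate appears in three other places in the SAP:
- Section 2.6.1.2 summarises the change from baseline to 6 hours after the first dose.
- Section 2.7.9 lists vital signs by patient, with abnormalities flagged where ranges exist.
- Table 4 gives criteria for notable vital signs, including pulse below 50 bpm.

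SAP section 3, on changes to protocol-specified analyses, reads as not applicable.

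**The concern.** The protocol defines this AESI by a number on a monitor, and the SAP counts it by a term on the adverse event page. The two agree only if every qualifying reading is also entered as an adverse event.

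Cardiac safety at treatment initiation is a secondary objective. Patients converting from fingolimod under Amendment 3 or later start directly at 2 mg, so that the role of titration can be studied. For that question the natural result is the proportion of patients whose heart rate fell below the protocol's limit after the first dose, by type of start. The plan does not produce it.

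**Working it through.** The plan gives no figure on this point, so the check is mainly a comparison of the texts.

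**1. Which limb of the definition matters.** Under protocol 8.4.2 a pre-dose heart rate below 55 bpm on Day 1 bars dosing, so the pre-dose limb should add no one to the Safety Set on that day. At later visits the documents do not label readings as pre-dose or post-dose. The operative limb is the Day 1 post-dose reading below 45 bpm.

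**2. Whether such a reading must become an adverse event.** Appendix 7 asks for additional monitoring when the 6-hour heart rate is below 45, even without symptoms. Neither it nor 10.2.3 tells the site to enter an asymptomatic reading on the adverse event page. Elsewhere the protocol is explicit: Appendix 3 requires new hypertension and all infections to be reported as adverse events, and Table 16-2 says to record the event for most liver criteria.

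**3. Whether another planned output supplies the count.**

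| Output | What it gives | Why it is not the count |
|---|---|---|
| SAP 2.7.3 | Patients with coded terms | No heart-rate rule |
| SAP 2.6.1.2 | Change at 6 hours, with minimum | A change is not a level: a fall of 10 bpm takes 55 to 45, but 75 only to 65 |
| SAP 2.7.9 listing | Individual values | Not a count; no 45 bpm flag is specified |
| SAP Table 4 | Patients with pulse below 50 | Different cut; section 2.7.9 names pulse and heart rate separately, and Table 4 has a criterion for pulse only |

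The liver AESI is a useful contrast. Protocol 10.2.1 also defines it by measurement ("Liver events of special interest (AESI) which consist of elevations of liver function tests (LFTs"), and the SAP at least has laboratory threshold criteria in Tables 2 and 3. Bradycardia has no counterpart at the protocol's post-dose cut.

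**4. The cuts.** Protocol 10.2.3 uses 55 pre-dose and 45 post-dose. Protocol Appendix 1 uses 55 for notable pulse. SAP Table 4 uses 50. Table 4 otherwise repeats Appendix 1, yet SAP section 3 reports no change.

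**5. Availability.** Table 8-1 marks the 6-hour Day 1 heart rate for recording in the clinical database.

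**6. Scale.**
- In the phase III trial described in protocol 1.1, 6% of siponimod patients had a reported bradycardia-type event. Here that would be 0.06 × 300 = 18 to 0.06 × 400 = 24 patients. These are reported events, not readings below 45.
- The number of readings below 45 cannot be derived, because the documents give no heart-rate mean or SD. As an illustration, assume a normal distribution, baseline mean 65 to 75, SD 9 to 13, and the phase III maximum mean Day 1 fall of 5.3 bpm. Then expected n = 300 × Φ((45 − (mean − 5.3))/SD).
  - Mean 75, SD 9: 300 × Φ(−2.74) = 0.9.
  - Mean 65, SD 13: 300 × Φ(−1.13) = 38.7.
  - With 50 in place of 45, the same two settings give 4.3 and 68.3, so Table 4's cut is no substitute.
- That model ignores the 55 bpm floor for dosing. With the floor and a uniform fall of 5.3, the lowest value is 55 − 5.3 = 49.7 and nobody is below 45. A dosed patient must fall by more than 55 − 45 = 10 bpm, about 1.9 times the mean fall (10/5.3). The answer depends on between-patient variation, which the documents do not give.
- A count of zero would still be informative. The exact two-sided 95% upper limit is 1 − 0.025^(1/300) = 1.2% for 300 patients and 1 − 0.025^(1/400) = 0.9% for 400.

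**The case against.** The strongest reply is that under-counting is only a risk. Since 10.2.3 calls a post-dose reading below 45 bradycardia and an AESI, a careful site should record it, and SAP 2.7.3 would then count it. Protocol 8.4 treats significant examination findings after consent as adverse events, and 8.4.2 sends clinically significant ECG abnormalities to the history or adverse event page. Every reading below 45 is also below 50, so if pulse in Table 4 covers the 6-hour reading, each case falls within that wider count.

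Much of this stands. It is wrong to say that low heart rates are absent from the SAP or that asymptomatic cases are sure to be lost. But the routes through significant findings rest on site judgment, and Table 4 cannot show who met the protocol's definition.

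A reader might also infer that a melanoma, or a case of progressive multifocal leukoencephalopathy (PML), would drop out of the AESI table. The documents do not support that as a certainty:
- The category names are broad, and the parentheses can be read as examples.
- Protocol 10.1.2 treats all malignant neoplasms as serious, and SAP 2.7.2 tabulates and lists serious events, so at most their place in one table is in doubt.
- Protocol 9.1.1 singles out malignancy for discontinuation ("such as malignancy (except successfully treated basal cell carcinoma"). That exempts one treated type from a rule; it does not rank tumours.
- The phase III death from "metastatic gastrointestinal melanoma within 4 months of commencing siponimod" is background, not an AESI designation.
- The protocol never calls PML an AESI. It appears in the Amendment 3 rationale as the reason for two natalizumab-related exclusions.

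**Conclusion.** The point holds for bradycardia. The protocol defines this AESI by heart rate, the SAP counts it by coded term, and no visible planned table gives the number of patients with a post-dose reading below 45 bpm. The mismatch between 45, 50 and 55 bpm is a plain inconsistency that SAP section 3 does not acknowledge.

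The size is unknown. The quantity that matters is the number of qualifying readings not also recorded as adverse events, and nothing in the documents fixes it. The illustration above runs from none to about 39 of 300 for all readings below 45, depending entirely on assumed distributions. The conclusion does not rest on that range. It rests on the visible text; SAP material redacted between sections 2.10 and 2.13 cannot be checked.

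The malignancy wording is a minor ambiguity to clear up. The documents do not support treating the absence of PML as a conflict with the protocol.

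**What to change.** In SAP 2.7.3, add a derived row for patients with a Day 1 post-dose heart rate below 45 bpm, as defined in protocol 10.2.3. Show it separately from bradycardia adverse event terms and combined with them (either one). Give n, % and an exact 95% CI, overall, by prior DMT, and by titrated versus direct 2 mg start. State the denominator as patients with a Day 1 post-dose reading, and report how many have none. Leave the pre-dose limb out of this row.

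Reconcile the 45, 50 and 55 bpm cuts across protocol 10.2.3, protocol Appendix 1 and SAP Table 4, say whether pulse and heart rate in SAP 2.7.9 are one variable, and record any intended difference in SAP section 3. Which cut should apply is for the sponsor to settle.

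As a minor clarification, state that malignancies means all malignant neoplasms, with basal cell carcinoma as a sub-row.

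The cost is SAP wording and one derived flag from data already collected. The downside is that the bradycardia count may come out slightly higher.

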#### **2.7.4 Deaths**

A listing for death including on treatment and post treatment deaths will be provided. The on-treatment period lasts from the date of first administration of study treatment to 30 days after the date of the last actual administrations of any study treatment.

#### **2.7.5 Laboratory data**

The summary of laboratory evaluations will be presented for the following groups of laboratory tests (hematology, clinical chemistry, serology, CYP2C9 Testing and [REDACTED]). Descriptive summary statistics for the change from Baseline to each study visit will be presented in the tabular form.

All laboratory data will be listed by patient and visit/time and if normal ranges are available abnormalities will be flagged.

In addition, shift tables will be provided for all parameters to compare a patient's Baseline laboratory evaluation relative to the visit's observed value. For the shift tables, the normal laboratory ranges will be used to evaluate whether a particular laboratory test value was normal, low, or high for each visit value relative to whether or not the Baseline value was normal, low, or high.

The following laboratory parameters will be analyzed:

**Hematology** will include red blood cell count, total and differential WBC count (basophils, eosinophils, lymphocytes, monocytes, neutrophils), platelet count, hemoglobin, hematocrit, mean corpuscular volume, mean corpuscular hemoglobin, mean corpuscular hemoglobin concentration and red blood cell morphology.

**Clinical Chemistry** will include electrolytes (Na, K, Cl, bicarbonate, Ca, Mg, P), random glucose, albumin, alkaline phosphatase, creatinine, ALT, AST, GGT, amylase, total bilirubin, conjugated bilirubin, total cholesterol, CRP, triglycerides, HDL and LDL.

Shift tables using the low/normal/high/ (low and high) classification will be used to compare Baseline to the worst on-treatment value.

**Table 2 Criteria for notable abnormalities**

Laboratory Variable SI Units	Standard Units	
LIVER FUNCTION AND RELATED VARIABLES		
SGOT (AST)	>82 U/L	>82 U/L
SGPT (ALT)	>90 U/L	>90 U/L
Gamma Glutamyltransferase (GGT)	> 130 U/L	> 130 U/L
Bilirubin (total)	>= 2.0 mg/dL	>= 34.2 mol/L
Alkaline phosphatase, serum	>280 U/L	>280 U/L
RENAL FUNCTION / METABOLIC AND ELECTROLYTE VARIABLES		
Glucose	>= 200 mg/dL	>= 11.11 mmol/L
Creatinine	>= 2.0 mg/dL	>= 176 umol/L
Amylase	>= 300 U/L	>= 300 U/L
Cholesterol (total)	>= 240 mg/dL	>= 6.21 mmol/L
Triglycerides	>= 300 mg/dL	>= 3.39 mmol/L
HEMATOLOGY VARIABLES		
Haemoglobin	<= 10.0 g/dL	<= 100 g/L
Platelet count (direct)	<= 100 k/mm 3	<= 100 x 10  /L
	>= 600 k/mm 3	>= 600 x 10  /L
WBC (total)	<= 2.0 k/mm 3	<= 2.0 x 10  /L
	>= 15 k/mm 3	>= 15 x 10  /L
HEMATOLOGY VARIABLES: DIFFERENTIAL		
Neutrophils (Seg. + Bands)	<= 1,000 /mm 3	<= 1 x 10 9 /L
	>= 12000/mm 3	>= 12 x 10 9 /L
Lymphocytes	< 200/mm 3	< 0.2 x 10 9 /L
	>= 8000/mm 3	>= 8 x 10 9 /L
RBC	< 3,300,000/mm 3	< 3.3 x 10 12 /L
	> 6,800,000/mm 3	> 6.8 x 10 12 /L

**Table 3 Criteria for abnormal criteria for by visit summaries**

Laboratory Variable (unit)	Criteria
Albumin (g/L)	<LLN
Bilirubin (direct/conjugated)(umol/L))	>ULN
	>2xULN
Gamma Glutamyltransferase (GGT)(U/L)	>ULN
	>3xULN
Glucose (mmol/L)	>ULN
Cholesterol (HDL) (mmol/L)	>ULN
Cholesterol (LDL) (mmol/L)	>ULN
SGOT (AST) (U/L)	>ULN
	>2xULN
	>3xULN
SGPT (ALT) (U/L)	>ULN
	>2xULN
	>3xULN
	>5xULN
Cholesterol (total) (mmol/L)	>ULN

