16.2 Appendix 2: Liver event definition and follow up requirements

Table 16-1 Liver Event and Laboratory Trigger Definitions

	Definition/threshold
LIVER LABORATORY	• 3 x ULN < ALT / AST ≤ 5 x ULN
TRIGGERS	• 1.5 x ULN < TBL ≤ 2 x ULN
LIVER EVENTS	ALT or AST > 5 × ULN
	 ALP > 2 × ULN (in the absence of known bone pathology)
	 TBL > 2 × ULN (in the absence of known Gilbert syndrome)
	ALT or AST > 3 × ULN and INR > 1.5
	 Potential Hy's Law cases (defined as ALT or AST > 3 × ULN and TBL > 2 × ULN (mainly conjugated fraction) without notable increase in ALP to > 2 × ULN)
	Any clinical event of jaundice (or equivalent term)
	 ALT or AST > 3 × ULN accompanied by (general) malaise, fatigue, abdominal pain, nausea, or vomiting, or rash with eosinophilia
	Any adverse event potentially indicative of a liver toxicity*

^{*}These events cover the following: hepatic failure, fibrosis and cirrhosis, and other liver damagerelated conditions; the non-infectious hepatitis; the benign, malignant and unspecified liver neoplasms TBL: total bilirubin; ULN: upper limit of normal

Table 16-2 Follow Up Requirements for Liver Events and Laboratory Triggers

Criteria	Actions required	Follow-up monitoring
Potential Hy's Law caseª	 Discontinue the study treatment immediately Hospitalize, if clinically appropriate Establish causality Record the AE and contributing factors (e.g., conmeds, med hx, lab) in the appropriate eCRF 	ALT, AST, TBL, Alb, PT/INR, ALP and GGT until resolution ^c (frequency at investigator discretion)
ALT or AST		
> 8 × ULN	 Discontinue the study treatment immediately Hospitalize if clinically appropriate Establish causality Record the AE and contributing factors (e.g., conmeds, med hx, lab) in the appropriate eCRF 	ALT, AST, TBL, Alb, PT/INR, ALP and GGT until resolution ^c (frequency at investigator discretion)
> 3 × ULN and INR > 1.5	 Discontinue the study treatment immediately Hospitalize, if clinically appropriate Establish causality 	ALT, AST, TBL, Alb, PT/INR, ALP and GGT until resolution ^c (frequency at investigator discretion)

Criteria	Actions required	Follow-up monitoring
	• Record the AE and contributing factors (e.g., conmeds, med hx, lab) in the appropriate eCRF	
	• Repeat LFT within 48 hours	
> 5 to ≤ 8 × ULN	• If elevation persists, continue follow-up monitoring	

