**Table 1 Assessment windows for scheduled visits**

Visit Name	Days	Scheduled Day of Visit	Visit Window
Screening	-28 Days	-28	-28 days to Day 1*
Baseline (Visit 1)	Day 1	1	Day 1 - 4
Visit 2	Day 7	7	Day 5 - 18
Visit 3	Day 28	28	Day 19 - 56
Visit 4	Day 84	84	Day 57 - 126
Visit 5/EOS	Day 168	168	Day 127 - 183
Follow up visits	Follow up visits	198	Day 184 - 205

Day 1\*: refers to the day 1 before dose administration.

For parameters which are not collected at every visit, visit windows defined in Table 1 will be combined. For example, if a parameter is measured at Day 28 and Day 84 only, Day 28 visit window will extend from Day 5 to Day 56 (combining Day 7 to Day 28 visit windows). If more than one assessment falls into the interval, the rules defined in [Section 2.1.1.5](#) below are applied.

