### 2.1.1.5 Multiple assessments within visit windows

When there are *multiple assessments* in a particular visit window, the following rules are applied to select one value “representing” the patient in summary statistics in a visit window (See **Table 1** ).

For Baseline assessment, definition see [Section 2.1.1.3](#). For post-Baseline visit windows the following applies (unless otherwise specified):

- For *quantitative variables*, the *closest* to the actual visit is chosen (if two assessments have the same distance, then the earlier one will be chosen);
- For *qualitative variables*, the *worst* record is selected. It is noted that in the analyses performed, *worst* case is always well defined.

In case qualitative variables are based on quantitative variables, the visit will be assigned to the quantitative variable, and this visit will be used for the derived qualitative variable.

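### No SAP table counts patients who meet the protocol's liver laboratory criteria at any time on treatment, and the by-visit Table 3 can miss peaks at off-schedule draws

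*SAP*

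**What the plan says.** Protocol Appendix 2 (Table 16-1) defines liver events in multiples of ULN. They include "ALT or AST > 5 × ULN", ALP >2×ULN, TBL >2×ULN, ALT or AST >3×ULN with INR >1.5, and potential Hy's Law, "defined as ALT or AST > 3 × ULN and TBL > 2 × ULN" without a notable ALP rise. Lower triggers are ALT/AST >3 to 5×ULN and TBL >1.5 to 2×ULN. Table 16-2 adds an action level at ALT/AST >8×ULN and asks for repeat tests within 48 hours or within a week, depending on the level.

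SAP 2.7.5 has two criteria tables. Table 3 is headed "Criteria for abnormal criteria for by visit summaries" and uses multiples of ULN. Table 2 uses fixed units, and no text says how it will be tabulated.

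SAP 2.1.1.5 governs what represents a patient in a visit window. For quantitative variables it is the assessment closest "to the actual visit is chosen (if two assessments have the same distance, then the earlier one will be chosen". For qualitative variables it is the worst record. Where a category derives from a quantitative value, "the visit will be assigned to the quantitative variable, and this visit will be used for the derived qualitative variable". Windows merge when a parameter is not collected at a visit. The SAP's own example is that the "Day 28 visit window will extend from Day 5 to Day 56", which fits the laboratory schedule because Visit 2 is no longer performed.

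SAP 2.7.9.1.2 gives vital signs an any-time section that includes unscheduled and premature-discontinuation visits. SAP 2.7.5 has no counterpart.

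**The concern.** Liver transaminase elevation is named in the protocol's risk section (4.5), and elevated liver tests are an adverse event of special interest (AESI) in both documents. The primary objective is overall safety. A reader of the clinical study report would expect to find how many patients crossed the protocol's own liver thresholds. As planned, the laboratory tables do not give that number for AST >5×ULN, TBL >2×ULN, ALP >2×ULN or potential Hy's Law. For the thresholds that Table 3 does include, the selection rule favours the scheduled draw over the higher one. The laboratory summary could therefore understate a named risk.

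**Working it through.** No design figure in the plan bears on this point, so there is none to reproduce. The check sets the tables side by side and then enumerates the selection rule.

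**Step 1. Coverage of the protocol criteria.**

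| Protocol criterion | SAP Table 3 | SAP Table 2 |
|---|---|---|
| ALT >5×ULN | present | ALT >90 U/L |
| AST >5×ULN | stops at >3×ULN | AST >82 U/L |
| ALT/AST >3×ULN | present for both | as above |
| ALP >2×ULN | no row | ALP >280 U/L |
| TBL >1.5× or >2×ULN | no row (direct bilirubin only) | TBL ≥2.0 mg/dL |
| Potential Hy's Law | none | none |
| ALT/AST >3×ULN with INR >1.5 | none | none |

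**Step 2. Can Table 2 stand in?** The documents give no ULN values, so these are assumptions.
- AST, ULN 35 to 45 U/L: the cut of 82 U/L is 82/35 = 2.3 to 82/45 = 1.8×ULN, while 5×ULN is 175 to 225 U/L.
- TBL, ULN 1.0 to 1.3 mg/dL: the cut of 2.0 mg/dL is 2.0 to 1.5×ULN.

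Table 2 would pool an AST above 5×ULN with values near 2×ULN, and it combines nothing.

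**Step 3. How often the closest-value rule drops an unscheduled draw.** Inputs are the windows in SAP Table 1 after merging (Day 5–56, 57–126, 127–183), nominal days 28, 84 and 168, and the protocol's ±5-day visit window. Distance is measured from the nominal day, and each window is assumed to hold one scheduled draw.
- Days available: 52 + 70 + 57 = 179. Less the three scheduled days, this is 176.
- Scheduled draw on the nominal day: nothing is closer, so 176 of 176 are dropped (100%).
- Scheduled draw 5 days early: the 9 days within ±4 of nominal win, and the tie at +5 goes to the earlier, scheduled draw. Kept: 9 × 3 = 27. Dropped: 176 − 27 = 149 (85%).
- Scheduled draw 5 days late: the same 9 days win, plus the tie at −5. Kept: 10 × 3 = 30. Dropped: 176 − 30 = 146 (83%).

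If distance is instead measured from the date on which the visit took place, the draw at that visit has distance zero and always wins.

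**Step 4. A concrete patient.** Tests are normal on Day 84, ALT is >5×ULN at an unscheduled draw on Day 110, and an early-discontinuation visit follows on Day 115. All three fall in Day 57–126. The distances from Day 84 are 0, 26 and 31. Table 3 keeps Day 84 and shows the patient as normal.

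**Step 5. Where that peak still appears.**
- Shift table to the worst on-treatment value (SAP 2.7.5): as high only. A value just above ULN and one above 5×ULN look alike.
- Laboratory listings: flagged, not counted.
- AE, AESI and SAE tables: by preferred term, if reported. Table 16-2 requires AE recording for potential Hy's Law, ALT/AST >5×ULN, isolated ALP or TBL >2×ULN, >3×ULN with INR >1.5 or with symptoms, and jaundice. It does not list AE recording for asymptomatic ALT/AST >3 to 5×ULN or TBL >1.5 to 2×ULN.

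**The case against.** The strongest reply is that the plan does not lose these patients. Worst-value shift tables cover ALT, AST, ALP and total bilirubin. All laboratory data are listed with flags. Appendix 2 makes AE recording mandatory for the more serious liver events, which should then reach the AESI or SAE tables. The protocol's laboratory section (12.5.1) promises listings, by-visit statistics and worst-value shifts, and the SAP delivers them. Table 16-1 was written for case management. The study is single-arm and descriptive, and its primary endpoint does not depend on Table 3.

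Most of this stands. A reader might infer that liver events go uncounted in the plan as a whole, and the documents do not support that. What remains is that none of these routes counts patients by threshold from laboratory values, and the AE route is not stated for the asymptomatic >3 to 5×ULN band.

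Two further points stand in part. First, an unscheduled value can win: with a scheduled draw on Day 80, a repeat 48 hours later on Day 82 is nearer to Day 84 and replaces it. It also wins if the scheduled draw is missing. Second, the sentence in 2.1.1.5 on derived variables might be read as assigning only the window and leaving the worst-record rule in force. Its place directly after the two rules, as a special case, makes that the less natural reading. Even on that reading, the rows missing in Step 1 stay missing.

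**Conclusion.** The point holds in a limited form. No SAP table counts patients meeting the Table 16-1 liver laboratory criteria at any time on treatment, and Table 3 can miss peaks at unscheduled or early-discontinuation draws. This is a reporting gap on a named risk. It does not affect the primary analysis or the sample size.

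The 83% to 100% in Step 3 describes the rule, not patients. It weights all days equally, whereas repeat tests cluster within days of a trigger, and it assumes one scheduled draw per window. A patient loses a Table 3 category only if the dropped value falls in a higher category than the retained one, and the documents give no rate for that.

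Two stronger inferences should be resisted. Applying the phase II figure of 4.3% with transaminases >3×ULN (Protocol 1.1) gives 0.043 × 300 = 12.9 to 0.043 × 400 = 17.2 patients. That is an illustrative number of elevations, not of missed patients: the rate comes from higher dose levels, and elevations at a retained scheduled draw are counted in Table 3. Nor do the documents show that the HDL row in Table 3 points the wrong way, since neither sets a direction of concern for HDL.

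**What to change.** Add to SAP 2.7.5 one patient-level table based on the worst on-treatment value from all scheduled, unscheduled and premature-discontinuation draws, as SAP 2.7.9.1.2 already does for vital signs. Count patients with:
- ALT or AST >3×, >5× and >8×ULN;
- ALP >2×ULN;
- TBL >1.5× and >2×ULN;
- potential Hy's Law: ALT or AST >3×ULN with TBL >2×ULN and ALP not >2×ULN;
- ALT or AST >3×ULN with INR >1.5, where INR is available.

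State whether the components of a combined criterion must come from the same draw, and say how Table 2 will be tabulated. Table 3 can stay as it is.

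The cost is one extra table from data already collected. The counts may be slightly less favourable than those in Table 3.
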